#### **9.4.4 Other Analyses**

Results of the exploratory endpoints (2D-TTE and biomarkers) and the change from baseline values (as applicable) will be listed and descriptively summarized by treatment and scheduled time point. Exploratory inferential comparisons to placebo may also be performed, if appropriate.

#### **9.4.5 Missing Data**

Data from subjects who withdraw from the study, including AEs and any follow-up, will be included in the analyses of all outcomes.

Missing data will be excluded from the analyses. No imputation will be performed, unless specified.

### **9.5 Interim Analyses**

No formal interim analyses are planned. Pharmacokinetic parameters will be calculated using available JK07 concentrations and scheduled sampling times to support JK07 dose escalation decisions, as applicable. Handling of the safety results obtained up to Day 15 after dose administrations will be described in the DRC Charter which will be prepared separately from the protocol.

## 9.6 Data Review Committee

A DRC consisting of members who are independent from the Sponsor will be established. The DRC will be composed of a minimum of 3 qualified cardiologists (independent voting members), and 3 non-voting members (including a biostatistician and Sponsor's medical monitor). When needed, ad hoc members or subject matter experts can be invited to participate as nonvoting participants. The DRC will have a separate charter from the protocol.

The DRC is responsible for reviewing and evaluating unblinded safety data for sentinel subjects, and blinded safety data (and safety data unblinded only on an as-needed basis) collected for at least 14 days and subsequently cumulatively at regularly scheduled meetings as defined in a separate DRC charter (minimum prior to each planned dose escalation). The DRC may also meet in ad hoc meetings at its discretion as needed in response to events occurring in the study. The DRC will be responsible for making recommendations as to whether it is scientifically and ethically appropriate to continue enrollment, discontinue treatment groups, or stop the study. Additional responsibilities for the DRC include initiation of enrollment at the next dose level. The DRC meetings will be documented in written meeting minutes.

In the first cohort, if no clinical effect is observed in the sentinel subject, the DRC will decide whether to proceed with the randomization of four additional subjects (3:1, JK07: placebo) to receive blinded IP. Once the last subject in the first cohort completes the evaluation period, which includes assessments through Day 15, the DRC will decide whether to proceed to the second cohort. The second cohort and subsequent cohorts will proceed as the first cohort until either of the following occur: a sentinel subject exhibits in the opinion of the DRC, a clinical effect (efficacy or safety observation), or a cohort exhibits, in the opinion of the DRC, a clinical effect.

Once a clinical effect is observed, the DRC may, at its discretion, expand the size of that cohort in which a clinical effect is first observed, and subsequent cohorts, up to a maximum of nine subjects (1 open-label JK07 sentinel subject, and 6:2 [JK07:placebo] randomized, double-blind subjects).

Following observation of a clinical effect and a decision to expand the size of the first cohort at which the clinical effect was observed, the DRC will decide whether to dose escalate after the last subject in the expansion cohort completes the evaluation period. If the DRC establishes to escalate the dose, a single unblinded sentinel subject will receive JK07 at the next dose level. If following the completion of the evaluation period of that sentinel subject the DRC decides to proceed, the remainder of the subjects in the expanded cohort size will receive JK07 or placebo according to the direction of the DRC, and this sequence will repeat until the highest planned dose level is reached or until the DRC determines not to dose escalate further.

During the review of the safety/tolerability results the DRC may make the determination to expand the size of the current cohort further, if not already at the maximum size, following which further dose escalation could proceed. Alternatively, the DRC may determine to decrease to a lower dose level with an additional cohort, which may be an intermediary dose or a pre-assigned cohort, which would include up to eight subjects randomized 6:2 [JK07: placebo], ~~with or~~ without an additional unblinded active sentinel subject. If the decision is to de-escalate to an intermediate dose between the prior cohort and the cohort at which dose escalation was halted, the cohort will comprise a single sentinel subject receiving JK07 followed by randomization of a minimum of 4 subjects (3:1, JK07: placebo) in the cohort. For any dose reduction to a dose below the highest established safe dose (i.e., below a dose for which the DRC approved expansion from a sentinel subject to enrollment of a full cohort), no sentinel subject will be required. Following a dose reduction, the DRC may subsequently decide to further reduce the dose level in a subsequent cohort of similar size or increase the dose in a subsequent cohort with or without the inclusion of a sentinel subject at the discretion of the DRC.

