The DRC will evaluate each sentinel subject as well as active treatment subjects in each dose cohort for DLAEs. To support dose escalation decisions by the DRC, safety, and tolerability results for all subjects in each cohort through at least Day 15 will be included in this review. During the review of the safety and tolerability results the DRC may make the determination to escalate to the next dose level or expand the size of the current cohort further, if not already at the maximum size, following which further dose escalation could proceed. Alternatively, the DRC may determine to decrease to a lower dose level which may be an additional cohort at an intermediary dose or a pre-assigned cohort. In the case that an intermediary dose is selected, a single sentinel subject will receive JK07 prior to randomization of the remaining subjects in the cohort. Following a dose reduction, the DRC may subsequently decide to further reduce the dose level in a subsequent cohort or increase the dose in a subsequent cohort. A sentinel subject is required only if the selected de-escalated dose is above the previously Highest Confirmed Safe Dose (HCSD).

At the time of the DRC safety review of the entire cohort, PK results if available for that cohort, will be evaluated (along with results of prior cohorts, as available).

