#### **4.6.2 Criteria for Stopping Dose Escalation**

The decision to stop dose escalation will be at the discretion of the DRC and all the criteria leading to this decision will be documented in the meeting minutes.

If the DRC decides not to dose escalate, the current cohort may be expanded, if not already at the maximum size, following which further dose escalation could proceed. If the decision is to de-escalate to the prior cohort, up to 8 subjects randomized (6:2, JK07:placebo), without an additional unblinded sentinel subject may be added to the cohort, after which, safety and tolerability will be reassessed. If the decision is to de-escalate to an intermediate dose between the prior cohort and the cohort at which dose escalation was halted, the cohort will comprise a single sentinel subject receiving JK07 followed by randomization of a minimum of 4 subjects (3:1, JK07:placebo) in the cohort. See [Section 9.6](#) for details regarding the number of subjects to be enrolled in de-escalated or intermediate de-escalated cohorts.

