## 6.3 Randomization and Blinding

All subjects other than sentinel subjects will be centrally assigned to randomized study treatment using an Interactive Voice/Web Response System (IVRS/IWRS). Before the study is initiated, the telephone number and call-in directions for the IVRS and/or the log in information & directions for the IWRS will be provided to each study center.

Subjects will be randomized to study treatment via stratified randomization. Separate randomization schedules will be used within each cohort (randomly permuted blocks within strata).

Blind Break (IVRS/IWRS)	The IVRS/IWRS will be programmed with blind-breaking instructions. In case of an emergency, the Investigator has the sole responsibility for determining if unblinding of a subject's treatment assignment is warranted. Subject safety must always be the first consideration in making such a determination. If the Investigator decides that unblinding is warranted, the Investigator should make every effort to contact the Trial Management Associate and Sponsor prior to unblinding a subject's treatment assignment unless this could delay emergency treatment of the subject. Under no circumstances should there be any delay in emergency treatment of a subject. If a subject's treatment assignment is unblinded, the Sponsor must be notified within 24 hours after breaking the blind. The date and reason that the blind was broken must be recorded in the source documentation and case report form (eCRF), as applicable.
Blinded FIH which may require unblinding subject/cohort	After each dose group, the DRC will determine the dosing regimen(s) for the next cohort. This decision will generally be made without breaking the randomization code. If judged necessary by the DRC, an individual or the complete cohort may be unblinded during evaluation of the study data. Before unblinding, a decision should be made about the action to be taken based on the revealed treatment allocation. The rationale for unblinding, etc., will be documented in meeting minutes.

Sentinel Subject	Each cohort at a new dose level higher than those previously tested shall have a single unblinded sentinel subject who will receive active treatment.
Unblinding by cohort	Thirty days following the decision by the DRC to dose escalate to a new dose level, unblinding of the previous cohort is permitted.

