**Figure 1 Study Schema**

The JK07 dose level of which are shown in [Table 1](#). The process above will proceed until the highest planned dose level (1.08 mg/kg) is reached or the DRC decides not to escalate dose further. Two additional higher cohorts may be added as per the DRC recommendation (total up to 7 cohorts with the highest JK07 dose administered not to exceed 2.5 mg/kg without further amending the protocol. DRC may decide to reduce the amount of dose in cohort 6 and cohort 7 based on the results of the previous cohorts. They may also decide to proceed with a cohort of decreased dose level (which may be pre-assigned dose level or not). Following a dose reduction, the DRC may

subsequently proceed with another cohort with reduced or increased dose level. A sentinel subject is required only if the selected dose level is above the previous Highest Confirmed Safe Dose (HCSD).

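### Protocol 9.6 counts a dose as established safe once its full cohort is opened, so after a safety halt there it waives the sentinel at an intermediate dose where 9.6, 4.6.2 and 1.1 require one

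*Protocol*

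**What the plan says.** Four parts of the protocol, and one of the SAP, bear on whether a lower-dose cohort after a halt needs a sentinel.

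- **Protocol 9.6, intermediate dose.** The rule opens "If the decision is to de-escalate to an intermediate dose between the prior cohort and the cohort at which dose escalation was halted" and goes on to require one JK07 sentinel, then at least 4 subjects randomized 3:1.
- **Protocol 4.6.2.** The same rule: "the cohort will comprise a single sentinel subject receiving JK07 followed by randomization of a minimum of 4 subjects". For a return to the prior cohort it gives a different option: "If the decision is to de-escalate to the prior cohort, up to 8 subjects randomized (6:2, JK07:placebo), without an additional unblinded sentinel subject".
- **Protocol 9.6, waiver.** The sentence right after the intermediate-dose rule says a sentinel is not needed for any reduction under the highest established safe dose, explained as "below a dose for which the DRC approved expansion from a sentinel subject to enrollment of a full cohort".
- **Protocol 1.1 (Treatment Groups and Duration).** "In the case that an intermediary dose is selected, a single sentinel subject will receive JK07 prior to randomization". Shortly after: "A sentinel subject is required only if the selected de-escalated dose is above the previously Highest Confirmed Safe Dose (HCSD").
- **Protocol 6.3.** "Each cohort at a new dose level higher than those previously tested shall have a single unblinded sentinel subject who will receive active treatment".
- **SAP IV.A.** "A sentinel subject is required only if the selected dose level is above the previous Highest Confirmed Safe Dose (HCSD"). The abbreviation lists of both documents spell out HCSD, but neither document defines it.

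Protocol 4.2 adds that escalation waits until the committee has evaluated safety data through Day 15 and the dose has been shown safe and well tolerated.

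**The concern.** The waiver's explanatory clause turns on one event, the Data Review Committee (DRC) letting the cohort go from its sentinel to full enrollment. That decision rests on one subject: 48 hours of data in 1.1, three days in 4.1, or the sentinel's evaluation period once cohorts have been expanded (1.1 and 9.6). The escalate-or-halt decision comes later and uses all subjects in the cohort through at least Day 15 (4.5). A halt at that regular review therefore always falls on a dose that already meets the clause. Read literally, the dose that has just raised the concern sets the ceiling under which no sentinel is needed.

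The stake is the safeguard described in 4.2: seeing a serious event in one subject before a whole cohort is exposed. This is a first-in-human study in patients with heart failure, and the gap would open just after a halt.

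**Working it through.** No figure in the plan is at issue, so the check applies each rule to one case.

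**Inputs.** Prior dose 0.27 mg/kg (Cohort 3) and halted dose 0.54 mg/kg (Cohort 4), from Protocol Table 4. Intermediate dose 0.40 mg/kg is assumed; any value between 0.27 and 0.54 gives the same answers.

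| Rule | Halt after the 0.54 sentinel only | Halt after the 0.54 full cohort was opened |
|---|---|---|
| 9.6 waiver | Highest opened dose is 0.27; 0.40 > 0.27, so no waiver | Highest opened dose is 0.54; 0.40 < 0.54, so sentinel waived |
| 9.6 intermediate-dose sentence, and 4.6.2 | Sentinel required | Sentinel required |
| 1.1 intermediary-dose sentence | Sentinel required | Sentinel required |
| 1.1 and SAP IV.A, HCSD rule | HCSD is 0.27; sentinel required | HCSD is 0.27 if it means passed Day 15 review: sentinel required. HCSD is 0.54 if it means what the 9.6 clause says: not required |
| 6.3 | 0.40 is not above the tested 0.54; no requirement | Same |

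The texts that address an intermediate dose agree in the first column. In the second, the waiver stands against the sentence before it, 4.6.2 and the 1.1 intermediary-dose sentence. The HCSD rule cannot settle it, because its outcome depends on which meaning is given to HCSD.

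**Exposure.**
- Waiver followed, cohort of eight at 6:2: up to 6 JK07 recipients with no lead-in.
- 4.6.2 followed: from 1 + 3 = 4 JK07 recipients of 5 subjects (minimum size) to 1 + 6 = 7 of 9 (maximum size), one of them dosed first and reviewed.

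**Dose position.** 0.40/0.54 = 0.74 of the halted dose, and 0.40/0.27 = 1.48 times the prior dose. On the planned steps, an intermediate dose is less than 3-fold above the prior dose if the halt is at Cohort 2 or 3 (0.09/0.03 = 0.27/0.09 = 3). It is less than 2-fold above if the halt is at Cohort 4 or 5 (0.54/0.27 = 1.08/0.54 = 2), or less than 3-fold if the DRC allows that larger step.

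**A second loose sentence in 9.6.** Earlier in the same paragraph, the option of up to eight randomized subjects with no further sentinel names an intermediary dose as well as a pre-assigned one. Section 4.6.2 gives that option only for the prior cohort.

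**The case against.** The case for leaving the text alone has four parts.

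1. *The waiver is permissive.* It says a sentinel is not needed; it does not bar one. Dosing a sentinel complies with the waiver, the intermediate-dose rule, 4.6.2 and 1.1 together, while omitting one breaches three of those. This stands. A reader might infer that the DRC is free to follow either rule. The documents do not support that, since only one course satisfies all of these sentences.
2. *The plain words already point the right way.* Safe, established and confirmed, read with 4.2, suggest a dose that passed review through Day 15. This supports treating the parenthetical as the outlier. It does not remove the error, because the parenthetical purports to say what the term means and says something else.
3. *The specific rule overrides the general one.* This is plausible, but the waiver comes last, covers any dose reduction, and no precedence between the two is stated. The SAP's statement that it prevails over the protocol does not help, since its own rule uses the undefined HCSD.
4. *The eight-subject sentence is a drafting remnant.* It carries visible struck-out words, and the lack of an additional sentinel fits a dose that already had one. That is a fair reading and a reason to tidy the sentence, not evidence of intent to skip the sentinel.

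The DRC charter, which was not available, may also settle the matter in practice. The protocol should still be consistent by itself.

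**Conclusion.** The parenthetical in 9.6 is wrong as written. It lets a dose at which escalation was halted for safety count as established safe, and so waives a sentinel that three other sentences require.

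The size is modest. The gap needs a halt after the full cohort was opened, the choice of an intermediate dose, and a DRC that uses the waiver despite 4.6.2. The dose is below one already given, though above the last dose whose full cohort passed review. In that event up to 6 JK07 recipients could start without a lead-in subject. The documents give no basis for a probability.

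A reader might also infer that the discretion in 9.6 over a sentinel on later re-escalation is the same error and should be withdrawn. The documents do not support that: 9.6 grants the discretion expressly, and 6.3 still requires a sentinel above any level already tested. Curing the parenthetical does not require narrowing it.

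The conclusion assumes that the explanatory clause is read as the meaning of the term, and that nothing in the unseen charter overrides it.

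**What to change.** In Protocol 9.6:

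- Replace the parenthetical with: *(HCSD, i.e., the highest dose whose full cohort completed DRC review through Day 15 and was judged safe and well tolerated)*. Let the waiver cover doses at or below it, to match 1.1.
- Add: *This waiver does not cover an intermediate dose, meaning one that lies between the prior cohort's dose and the dose where escalation was halted; such a cohort requires one sentinel subject.*
- Limit the eight-subject option without a sentinel to the prior dose or a lower pre-assigned dose, in line with 4.6.2.

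In Protocol 1.1 and SAP IV.A, use the same meaning of HCSD and point to 9.6 for the intermediate-dose exception. The pointer matters because 4.6.2 does not limit halts to safety reasons: a dose could be judged safe and still be where escalation stopped.

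**Cost.** Relative to 4.6.2, wording only. Relative to the waiver, one lead-in JK07 subject and a wait for that subject's data: 48 hours (1.1) or three days (4.1), up to the evaluation period through Day 15 once cohorts have been expanded. One sentinel plus eight randomized is 1 + 8 = 9, within the 9-subject cohort maximum.

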## 11.0 APPENDICES

### Appendix 1      Cancer Screening Guidelines

#### AMERICAN CANCER SOCIETY GUIDELINES FOR THE EARLY DETECTION OF CANCER

Screening tests are used to find cancer before a person has any symptoms. Here are the American Cancer Society's recommendations to help guide you when you talk to your doctor about screening for certain cancers.

##### Breast cancer

- **Women ages 40 to 44** should have the choice to start annual breast cancer screening with mammograms (x-rays of the breast) if they wish to do so.
- **Women age 45 to 54** should get mammograms every year.
- **Women 55 and older** should switch to mammograms every 2 years or can continue yearly screening.
- Screening should continue as long as a woman is in good health and is expected to live 10 more years or longer.
- **All women** should be familiar with the known benefits, limitations, and potential harms linked to breast cancer screening.

Women should also know how their breasts normally look and feel and report any breast changes to a health care provider right away.

Some women – because of their family history, a genetic tendency, or certain other factors – should be screened with magnetic resonance imaging (MRIs) along with mammograms (the number of women who fall into this category is very small.) Talk with a health care provider about your risk for breast cancer and the best screening plan for you.

##### Colon and rectal cancer and polyps

For people at average risk for colorectal cancer, the American Cancer Society recommends starting regular screening at **age 45**. This can be done either with a sensitive test that looks for signs of cancer in a person's stool (a stool-based test), or with an exam that looks at the colon and rectum (a visual exam). Talk to your health care provider about which tests might be good options for you, and to your insurance provider about your coverage. No matter which test you choose, the most important thing is to get screened.

If you're in good health, you should continue regular screening through **age 75**.

For people **ages 76 through 85**, talk with your health care provider about whether continuing to get screened is right for you. When deciding, take into account your own preferences, overall health, and past screening history.

People **over 85** should no longer get colorectal cancer screening.

If you choose to be screened with a test other than colonoscopy, any abnormal test result needs to be followed up with a colonoscopy.

##### Cervical cancer

- **Cervical cancer testing should start at age 21.** Women under age 21 should not be tested.

- **Women between the ages of 21 and 29** should have a Pap test done every 3 years. HPV testing should not be used in this age group unless it's needed after an abnormal Pap test result.
- **Women between the ages of 30 and 65** should have a Pap test plus an HPV test (called "co-testing") done every 5 years. This is the preferred approach, but it's OK to have a Pap test alone every 3 years.
- **Women over age 65** who have had regular cervical cancer testing in the past 10 years with normal results should not be tested for cervical cancer. Once testing is stopped, it should not be started again. Women with a history of a serious cervical pre-cancer should continue to be tested for at least 20 years after that diagnosis, even if testing goes past age 65.
- **A woman who has had her uterus and cervix removed (a total hysterectomy)** for reasons not related to cervical cancer and who has no history of cervical cancer or serious pre-cancer should not be tested.
- **All women who have been vaccinated against HPV** should still follow the screening recommendations for their age groups.

Some women – because of their health history (HIV infection, organ transplant, DES exposure, etc.) – may need a different screening schedule for cervical cancer. Talk to a health care provider about your history.

### **Endometrial cancer**

The American Cancer Society recommends that at the time of menopause, all women should be told about the risks and symptoms of endometrial cancer. Women should report any unexpected vaginal bleeding or spotting to their doctors.

Some women – because of their history – may need to consider having a yearly endometrial biopsy. Please talk with a health care provider about your history.

